5.4.1 Radiographic Assessments

Baseline assessments should be performed within 28 days prior to the first dose, utilizing FDG PET-CT, CT or MRI. CT scans are preferred for CTCL. In addition to chest, abdomen, pelvis, all known sites of disease should be assessed at baseline. FDG PET-CT will be performed for assessment throughout the study for subjects with DLBCL, PTCL, PMBL and MGZL. Low dose or attenuation correction CT portions of a combined FDG PET-CT are of limited use in anatomically based efficacy assessments and it is therefore suggested that they should not be substituted for dedicated diagnostic contrast enhanced CT scans for anatomically based measurements. However, if a site can document that the CT performed as part of a FDG PET-CT is of identical diagnostic quality to a diagnostic CT with oral contrast, (+/- IV contrast) then the adequate dose CT of the FDG PET-CT can be used for tumor measurements. Subjects with CTCL are to perform the CT scans described above in addition to medical photographs if appropriate for disease assessment.

Subjects will be evaluated for tumor response by FDG PET-CT, or CT/MRI at week 6 and week 12 continuing every 9 weeks (+/- 1 week) for the subsequent 4 tumor assessment timepoints, regardless of dosing schedule. After the first year, tumor assessments are to occur every 12 weeks (+/- 2 weeks) until disease progression is documented.

Tumor assessments for ongoing study treatment decisions will be completed by the investigator using the Lugano Classification 2014 for Diffuse Large B Cell Lymphomas and Peripheral T Cell Lymphomas. Refer to [Appendix 2](#) for further details. For Cutaneous T Cell Lymphomas, response

should be assessed by the consensus Global Response Score. Refer to [Appendix 4](#) for further details.

5.4.2 Assessment of Overall Tumor Burden and Measurable Disease

To serially evaluate tumor response to therapy, it is necessary to estimate the overall tumor burden at baseline and use this as a comparator for subsequent measurements. Measurable disease is defined by the presence of at least one measurable tumor lesion.

At baseline, tumor lesions/lymph nodes will be categorized as measurable or non-measurable as follows in Section 5.4.2.1 and Section 5.4.2.2.

5.4.2.1 Measurable Lesions

Measurable lesions must be accurately measured in at least two perpendicular dimensions. For subjects staged with PET-CT (DLBCL, PTCL, PMBL and MGZL), focal uptake in nodal and extranodal sites that is in keeping with lymphoma, according to the distribution and/or CT characteristics, is considered involvement with lymphoma, including spleen, liver, bone, thyroid, and so on. For subjects staged with CT, up to six of the largest target nodes, nodal masses, or other lymphomatous lesions that are measurable in two diameters (longest diameter [LDi] and shortest diameter) should be identified from different body regions representative of the patient's overall disease burden and include mediastinal and retroperitoneal disease, if involved. A measurable node must have a LDi greater than 15 mm. Measurable extranodal disease (eg, hepatic nodules) may be included in the six representative, measured lesions. For extranodal measurable lesion the LDi must be greater than 10 mm. All other lesions (including nodal, extranodal, and assessable disease) should be followed as non measurable disease (eg, cutaneous, GI, bone, spleen, liver, kidneys, pleural or pericardial effusions, ascites). In subjects in whom a discordant histology or malignant transformation is suspected, a PET-CT may identify the optimal site to biopsy for confirmation.

For subjects with CTCL measurable, skin lesions are defined as papules, plaques and patches covering $\geq 10\%$ of the skin surface (T2). Lymph nodes are qualified as abnormal if > 15 mm in diameter.

5.4.2.2 Non-Measurable Lesions

Non-measurable lesions will be all other lesions, including small lymph nodes (longest diameter ≤ 15 mm) as well as truly non-measurable lesions. Lesions considered truly non-measurable include: leptomeningeal disease, ascites, pleural or pericardial effusion, inflammatory breast disease, lymphangitic involvement of skin or lung, abdominal masses/abdominal organomegaly identified by physical exam and that is not measurable by reproducible imaging techniques.

5.4.3 Specifications by Method of Assessment

5.4.3.1 Measurement of Lesions

All measurements should be recorded in the eCRF in metric notation (mm). All baseline evaluations should be performed as close as possible to the treatment start and never more than 28 days before the beginning of treatment.

5.4.3.2 Method of Assessment

The same method of assessment and the same technique should be used to characterize each identified and reported lesion at baseline and during follow-up. Imaging based evaluation should always be done rather than clinical examination unless the lesion(s) being followed cannot be imaged but are assessable by clinical exam.

5.4.3.3 FDG PET-CT, CT Scan and MRI

Contrast-enhanced Computed Tomography (CT) scans acquired on dedicated CT equipment are preferred for response assessment of subjects with CTCL or DLBCL/PTCL/PMBL/MGZL subjects without FDG avid tumors in this study. CT with contrast of the chest, abdomen and pelvis (as clinically indicated) are to be performed for tumor assessments at week 6 and week 12 continuing every 9 weeks (+/- 1 week) for the subsequent 4 tumor assessment timepoints, regardless of dosing schedule. After the first year, tumor assessments are to occur every 12 weeks (+/- 2 weeks) until disease progression is documented. CT scans should be acquired with 5mm slices with no intervening gap (contiguous). When CT scans have slice thickness greater than 5 mm, the minimum size for a measurable lesion should be twice the slice thickness.

Should a subject have a contraindication for CT IV contrast, a non-contrast CT of the chest and a contrast enhanced MRI of the abdomen and pelvis may be obtained. MRIs should be acquired with slice thickness of 5 mm with no gap (contiguous).

Every attempt should be made to image each subject using an identical acquisition protocol on the same scanner for all imaging time points.

FDG PET-CT with oral contrast and intravenous contrast will be performed for assessment throughout the study for patients with DLBCL, PTCL, PMBL and MGZL. If however CT is low dose and intravenous contrast is not available, then sites may obtain additional CT with oral and intravenous contrast.

Note on CT component of a PET-CT scanner: Combined modality scanning such as with PET-CT is increasingly used in clinical care. Low dose or attenuation correction CT portions of a combined PET-CT are of limited use in anatomically based efficacy assessments and it is therefore suggested that they should not be used. Site should document that the CT performed as part of a PET-CT is of identical diagnostic quality to a diagnostic CT (with IV and oral contrast). In certain cases where the CT portion of the PET-CT scan is low dose, then a diagnostic CT scan with oral and intravenous contrast should be performed.

MRI of the brain should be done at baseline if CNS involvement is suspected to rule out active disease. Scans during on-study treatment and follow up periods are required only as clinically indicated for new signs and symptoms that suggest central nervous system (CNS) involvement.

5.4.3.4 Clinical Lesions

Clinical lesions (nodal, extranodal) will only be considered measurable when they are superficial and ≥ 15 mm diameter as assessed using calipers. As previously noted, when lesions can be evaluated both by clinical exam and imaging, imaging evaluation should be undertaken since it is more objective.

In regards to CTCL, skin evaluation will be performed using the m SWAT scoring system. It is recommended that the mSWAT at the bedside should be performed by the same investigator at all time points. If the same investigator cannot perform all the assessments, then all personnel grading the same patient must have completed prior training, ideally before study initiation.

5.4.3.5 Medical Photography (Skin lesions only)

Medical photography with ruler measurements for documentation of skin lesions are recommended in subjects with CTCL.

5.4.3.6 Whole Blood (SS-CTCL only)

Peripheral blood flow cytometry to evaluate for SS cell at screening and at response confirmation is required in subjects with CTCL(SS).

5.4.3.7 Target Lesions

At baseline, up to 6 of the largest dominant nodes or nodal masses meeting the criteria for measurable lesions given in [Section 5.4.2](#) should be identified as target lesions and their measurements recorded. Other measurable lesions will be designated as non-target lesions.

A sum of the product of the diameters (SPD) will be calculated for all target lesions and recorded as the baseline SPD. The baseline SPD will be used as reference to further characterize any objective tumor regression in the measurable dimension of the disease.

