 - (1) PTCL must be relapsed and/or refractory disease after 1 or more lines of standard systemic therapy
- iii) CTCL (MF/SS subtypes only) with diagnosis of MF/SS by immunopathological and molecular, biological criteria
 - (1) CTCL must be relapsed and/or refractory disease after 1 or more lines of standard systemic therapy
 - (2) Stage IB-IV per TNMB modified International Society of Cutaneous Lymphoma (ISCL) and WHO-EORTC staging criteria ([Appendix 3](#)).
- iv) PMBL must be relapsed/refractory disease after high-dose conditioning chemotherapy and ASCT, or subjects with relapsed and/or refractory PMBL after at least 2 prior multi-agent chemotherapy regimens if ASCT ineligible
- v) MGZL must be relapsed/refractory disease after high-dose conditioning chemotherapy and ASCT, or subjects with relapsed and/or refractory MGZL after at least 2 prior multi-agent chemotherapy regimens if ASCT ineligible
- e) Evaluable tumor tissue (archived or new biopsy) must be provided for biomarker analysis as FFPE tumor block or a minimum of 20 slides. Bone marrow aspirate and biopsy and peripheral blood are not to be submitted for evaluable tumor tissue. In order to be treated, the sample must meet the minimum quality requirements, as determined by the central laboratory during the screening period.
- f) All subjects with PTCL, DLBCL, PMBL and MGZL must have measurable disease defined as:
 - i) At least 1 measurable site of disease according to the Lugano Classification 2014 ([Appendix 2](#)). (Criteria does not apply for CTCL).
- g) Subject Re-enrollment: This study permits the re-enrollment of a subject that has discontinued the study as a pre-treatment failure (ie, subject has not been treated). If re-enrolled, the subject must be re-consented.

3. Physical and Laboratory Test Findings

- a) Screening laboratory values must meet these following criteria:
 - i) Absolute neutrophil count (ANC) $\geq 1.0 \times 10^9$ cells/L (ie, $\geq 1000/\mu\text{L}$)
 - ii) Platelets $\geq 50 \times 10^9$ cells/L (ie, $\geq 50,000/\mu\text{L}$) without transfusion support within 14 days prior to test
 - iii) Hemoglobin ≥ 8.5 g/dL without transfusion support within 7 days prior to test

- iv) Alanine aminotransferase (ALT) and aspartate aminotransferase (AST) ≤ 2.5 x upper limit of normal (ULN)
- v) Serum bilirubin ≤ 1.5 X ULN (unless due to Gilbert's syndrome, in which case the cut off is < 3.0 x ULN)

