5.4.3.8 Non-Target Lesions

All other lesions (or sites of disease) including non-measurable lymph nodes should be identified as non-target lesions and should also be recorded at baseline. Measurements are not required and these lesions should be followed as ‘present’, ‘absent’, or in rare cases ‘unequivocal progression’. In addition, it is possible to record multiple non-target lesions involving the same organ as a single item on the case report form (eg, ‘multiple enlarged pelvic lymph nodes’ or multiple liver nodules’).

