 - b) CT based response: Target node/nodal masses must regress to ≤ 1.5 cm in LDi, with no extralymphatic sites of disease.

Organ involvement: Absence of organomegaly (Table 3).

- 2) Bone marrow: No evidence of FDG-avid disease in marrow. If there was evidence of involvement of bone marrow with lymphoma at screening/baseline and a biopsy was performed (PTCL), a bone marrow biopsy will be required to confirm CR.
- 3) The presence of residual symptoms in the absence of detectable disease by imaging does not preclude the designation of CR.

PR (Partial Remission)

The designation of PR requires all of the following:

- 1) PET-CT based response: Score of 4 or 5, provided reduced uptake compared with base line and absence of structural progression development on CT Scan.

- 2) CT based response: $\geq 50\%$ regression in SPD of upto 6 measurable nodal and extranodal lesions (Table 3) .
- 3) Splenic and hepatic nodules must regress by $\geq 50\%$ in length beyond normal.

Bone marrow : reduced uptake compared with baseline. If there is evidence of nodal response but persistent focal changes in the marrow consider further evaluation (Table 3).

SD (Stable Disease)

SD is defined as the following:

- 1) PET-CT based response: no metabolic response, score of 4 or 5 with no significant changes from baseline.
- 2) CT based response: $< 50\%$ decrease from baseline, absence of new lesions (Table 3).
- 3) Bone marrow: no change from baseline.

PD: Relapsed Disease (after CR)/Progressive Disease (after PR, SD)

- 1) PET-CT based response: Score of 4 or 5 with increase in intensity from baseline or interim scan/ or any new FDG avid focus consistent with malignant lymphoma (Table 3).
- 2) CT based response: New node, new or recurrent splenomegaly, progression of existing lesions (Table 3).

IR (INDETERMINATE RESPONSE)

A patient will be considered to have Indeterminate Response (IR) in one or more of the 3 following circumstances

- 1) Increase in overall tumor burden (as assessed by SPD) of $\geq 50\%$ of up to 6 measurable lesions in the first 12 weeks of therapy, without clinical deterioration (IR(1))
- 2) Appearance of new lesions; or growth of one or more existing lesion(s) of $\geq 50\%$ at any time point during treatment occurring in the context of lack of overall progression ($<50\%$ increase) of overall tumor burden, as measured by SPD of up to 6 lesions at any time during the treatment (IR(2))

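### Protocol 5.4.3.7 limits target lesions to nodes, contradicting 5.4.2.1 and Appendix 2, so CT-based partial response in extranodal-only disease depends on which passage the site follows

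*Protocol*

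**What the plan says.** - **Eligibility.** Protocol 3.3.1, criterion 2(f), for DLBCL, PTCL, PMBL and MGZL: "At least 1 measurable site of disease according to the Lugano Classification 2014". The site need not be nodal. CTCL is exempt from this criterion and lies outside the point.
- **Measurability.** Protocol 5.4.2.1: "For extranodal measurable lesion the LDi must be greater than 10 mm". For subjects staged with CT, the same section says: "Measurable extranodal disease (eg, hepatic nodules) may be included in the six representative, measured lesions".
- **Target lesions.** Protocol 5.4.3.7 selects "up to 6 of the largest dominant nodes or nodal masses meeting the criteria for measurable lesions" and continues: "Other measurable lesions will be designated as non-target lesions". The baseline SPD is the sum over target lesions.
- **Non-target lesions.** Protocol 5.4.3.8: "Measurements are not required and these lesions should be followed as" present, absent or, rarely, unequivocally progressing.
- **Response criteria.** In Appendix 2, the CT column of Table 1, the table's footnote on measured lesions and the PR narrative all count extranodal lesions among the up to six. The narrative opens: "The designation of PR requires all of the following". It then lists a PET-CT item, a CT/SPD item and a splenic and hepatic item.
- **Modality.** Protocol 5.4 derives response mainly from FDG PET-CT. Subjects with avid lesions are followed by PET, and those with non-avid lesions by CT.

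**The concern.** Two parts of the protocol give different answers to one question: can an extranodal lesion be a target lesion? Section 5.4.3.7 carries the title a site would look up when choosing targets, and read alone it says no. The reference there to 5.4.2 does not resolve the conflict. It brings in the size criteria, but the sentence still names only nodes and nodal masses, and the next sentence makes every other measurable lesion non-target.

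The primary efficacy endpoint is investigator-assessed ORR, and central scan review is optional under Protocol 5.3.1. A difference between sites in choosing targets may therefore never be harmonised. The people exposed are enrolled subjects with measurable extranodal disease and no measurable node. One site would give them an SPD and another would not. The baseline tables of target-lesion presence, site and SPD in SAP 7.3.2 carry the same ambiguity.

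**Working it through.** The plan states no figure on this point, so the check is mainly textual.

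**1. Can an extranodal-only subject enrol?** Yes. Criterion 2(f) needs one measurable site, and 5.4.2.1 makes an extranodal lesion measurable when its longest diameter exceeds 10 mm.

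**2. Does that subject have a baseline SPD?**
- Under 5.4.3.7 and 5.4.3.8: no. There are no nodal targets, the lesion is non-target and need not be measured, and the sum has no terms.
- Under 5.4.2.1 and Appendix 2: yes. The lesion can be one of the six.

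**3. Can that subject be scored PR?**
- *Followed by CT, using 5.4.3.7:* no. CT-based PR in Table 1 needs an SPD decrease of at least 50%, and there is no baseline SPD to compare with. CR stays reachable because it needs no baseline SPD.
- *Followed by CT, using 5.4.2.1 and Appendix 2:* yes, by the ordinary SPD comparison.
- *Followed by PET, using Table 1:* yes. The PET column asks for a score of 4 or 5 with uptake lower than at baseline, whatever the size of the residual mass. SPD plays no part.
- *Followed by PET, with the Appendix 2 narrative read as a conjunction:* the SPD item would also apply, and the subject would be back in the first case.

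**4. Effect of one misclassified subject.** ORR is responders divided by treated subjects, so one lost PR moves it by 1/N:
- B1: 1/40 = 2.5 points
- B2 and B4: 1/30 = 3.3 points
- B5: 1/10 = 10 points

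**5. Illustration of scale in B1, under stated assumptions.** First, the plan's power. Take the smallest r with P(X ≥ r | n = 40, p = 0.40) ≤ 0.10. This gives r = 21, with exact alpha 0.074 and power 0.870 at a true ORR of 0.60, matching the 87% in Protocol 8.1.

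Now let f be the share of B1 that can never be scored PR for this reason, and assume that PRs are two thirds of responses. Neither value is in the documents. Scored ORR = 0.60 × (1 − f × 2/3), and power = P(X ≥ 21 | 40, scored ORR):
- f = 5% (2 of 40): ORR 0.58, power 0.81
- f = 10% (4 of 40): ORR 0.56, power 0.73
- f = 20% (8 of 40): ORR 0.52, power 0.54

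f is a compound share. The subject must have extranodal-only measurable disease, must have a PR that depends on SPD, and must be at a site that follows 5.4.3.7. It is therefore smaller than the share with extranodal-only disease, and the larger values are upper-end illustrations.

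**The case against.** The strongest reply is that Appendix 2 governs. Protocol 5.4.5 and 8.3.1 both send response evaluation there, and Appendix 2 takes the SPD over nodal and extranodal lesions. On that view 5.4.3.7 is loose wording and these subjects do have an SPD. This stands as far as it goes: a reader should not conclude that extranodal-only subjects definitely cannot be scored PR. It does not remove the contradiction, because no passage ranks the sections and a site choosing targets from 5.4.3.7 would not measure the lesion.

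A second reply is that most response calls rest on PET, where PR needs no SPD. This also stands and confines the clear problem to CT-followed, non-avid disease. Joining the PET and CT items of the narrative is the weaker reading. The items are labelled by modality, as in the columns of Table 1. A literal conjunction would also require splenic and hepatic regression of everyone and deny PR to CT-followed subjects without a PET score. Still, the opening words permit it.

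Three stronger inferences are tempting but not supported:
- *That in mixed disease nodal shrinkage alone yields PR while a dominant extranodal mass is unchanged.* The CT column of Table 1 also requires nonmeasured lesions to be absent, normal or regressed, without increase, and the narrative requires at least 50% regression of splenic and hepatic nodules.
- *That every CT-followed subject is affected.* Those with nodal disease only are not.
- *That the indeterminate-response rules cannot be applied.* IR(1) is defined on up to six measurable lesions, not on 5.4.3.7 targets, and IR(2) adds new or growing lesions to the target set. IR is also exploratory.

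**Conclusion.** The contradiction is real. Section 5.4.3.7 as written conflicts with 5.4.2.1 and Appendix 2 on whether extranodal lesions enter the SPD, and 2(f) admits subjects for whom the answer decides whether an SPD exists. For such a subject followed by CT, PR is attainable under one passage and unattainable under the other. For PET-followed subjects there is no effect unless the narrative is read as a conjunction.

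The size is known only per subject: 2.5 points of ORR in B1, 3.3 in B2 or B4 and 10 in B5 for each misclassified partial responder. The number of such subjects cannot be derived from the documents, and the power figures above depend on assumed shares. The error runs toward understating ORR at sites that follow 5.4.3.7. It deserves correction because it touches the primary endpoint and costs little to remove. It does not show that the trial's ORR would be materially wrong.

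**What to change.** 1. Reword the first two sentences of 5.4.3.7 to match 5.4.2.1 and Appendix 2. Up to six of the largest measurable nodes, nodal masses and extranodal lesions are targets and are measured. Measurable lesions beyond six, and non-measurable sites, are non-target.
2. State in the Appendix 2 PR narrative that the PET-CT and CT items apply according to the modality by which the subject is followed, as in Table 1.

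The cost is a short protocol clarification. The CRF is not among the documents, so its target-lesion entry should be checked to confirm that it accepts an extranodal site. No new imaging is needed. Protocol 5.4 requires sites to keep on-study scans available, so targets already chosen under the narrower wording can be re-measured.

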5.4.3.8 Non-Target Lesions

All other lesions (or sites of disease) including non-measurable lymph nodes should be identified as non-target lesions and should also be recorded at baseline. Measurements are not required and these lesions should be followed as ‘present’, ‘absent’, or in rare cases ‘unequivocal progression’. In addition, it is possible to record multiple non-target lesions involving the same organ as a single item on the case report form (eg, ‘multiple enlarged pelvic lymph nodes’ or multiple liver nodules’).

5.4.4 Bone Marrow Assessments

Bone marrow assessments are not mandatory in the study, unless clinical suspicion is high. In subjects with PTCL, if there is clinical suspicion for bone marrow involvement, it is recommended

to obtain a bone marrow aspirate and biopsy at the time of screening. All subjects may volunteer to undergo bone marrow biopsy and aspirate at any time during therapy if clinically indicated for DLBCL, CTCL, PMBL and MGZL.

Only if clinically indicated, bone marrow biopsy and aspirate performed within 90 days prior to obtaining consent or fresh sample collected during screening are acceptable options. If a bone marrow biopsy/aspirate is performed during the screening period, consider submitting a bone marrow aspirate sample for biomarker analyses. For subjects that perform bone marrow assessment at screening and there is marrow involvement confirmed, a bone marrow biopsy and aspirate will be required to confirm a CR, and submission of bone marrow aspirate samples is optional as detailed in [Table 5.6-1](#).

In addition to efficacy assessments, additional, optional, bone marrow biopsy and aspirate samples may be collected and submitted for biomarker studies as detailed in [Table 5.6-1](#).

